#### **5.8.3** Secondary Safety Endpoints

#### 5.8.3.1 Composite 30-Day Secondary Safety Endpoint

**Table 2** lists the event rates assumed for the components of the composite secondary safety endpoint in the Device group.

Tuble 2. Hisbumptions for Secondary Surety Event Rates at 20 Buys		
Event	Device Group	
Death	5%	
Stroke	2%	
MI	2%	
Non-elective CV Surgery for	3%	
Device Related Complications		
Total	12%	

Table 2: Assumptions for Secondary Safety Event Rates at 30 Days

Two thousand (2000) simulations were performed. A total of 305 subjects in the Device group (without attrition) provides > 95% power to reject the null hypothesis at the one-sided significance level of 5%.

#### 5.8.3.2 All-Cause Mortality at 12 Months

Two thousand (2000) simulations were performed. Assuming 27% mortality in the Control group, 22% mortality in the Device group, and 7.5% attrition in both groups at 12 months, a total of 610 subjects will provide > 90% power to reject the null hypothesis at the one-sided significance level of 5%.

#### 5.8.4 Secondary Effectiveness Endpoints

Unless otherwise specified, the power calculations of the following secondary effectiveness endpoints are based on the two-sided significance level of 5%.

#### 5.8.4.1 Change in KCCQ QoL score at 12 Months

A simulation was performed. Based on the following assumptions, the power is > 90% to reject the null hypothesis at the 5% significance level.

- Subjects in the Device group have 8 points more improvement in the mean change of KCCQ score at 12 months from baseline than subjects in the Control group, with standard deviation (SD) of 25 points for the mean change in KCCQ score in each group.
- Assume all-cause mortality rate at 12 months is 27% in the Control group, and 22% in the Device group. Approximate 70% of all-cause deaths in each group are due to cardiovascular reasons. Furthermore, about 70% of cardiovascular deaths are HF related. Thus, it is expected to have approximate 3% difference in HF related cardiovascular deaths at 12 month between two treatment groups (i.e. 10% in the Device group and 13% in the Control group). Subjects who experienced heart failure death prior to 12 months follow-up are assigned with the lowest KCCQ score at 12 months

- 10% attrition rate in both groups due to withdrawn or missed visit at 12 months.
- Two-sample t-test (it is anticipated that an ANCOVA analysis adjusting for baseline values provides as much as or more power than a two-sample t-test  $^{9,10}$ ).

#### 5.8.4.2 MR severity at 12 Months

Sample size calculation for the MR severity at 12 months was performed using NCSS PASS 11 (Hintze, J., 2011, NCSS, LLC. Kaysville, Utah).

The power calculation for the MR severity at 12 months is based on the following assumptions:

- At least 20% more subjects in the Device group had  $MR \le 2+$  at 12 months than those subjects in the Control group.
- Assume all-cause mortality rate at 12 months is 27% in the Control group, and 22% in the Device group.
- 20% attrition rate in both groups due to withdrawn, missed visit, or unevaluable echocardiography at 12 months.
- Fisher's exact test at the 5% level of significance

With the effective sample size of total 300 subjects at 12 months, there is >90% power to demonstrate that the Device group has achieved more MR  $\leq$ 2+ at 12 months than the Control group.

# 5.8.4.3 Hierarchy of death and recurrent HF hospitalization (analyzed when the last subject completes 12 months of follow-up)

A simulation was performed. Based on the same assumptions as stated from the primary effectiveness endpoint, and Finkelstein-Schoenfeld Analysis method for the hierarchy of death and recurrent HF hospitalization, a total sample size of 610 subjects provides approximate 84% power to detect 10% absolute difference in all-cause mortality (i.e. 29% for the Control group and 19% for the Device group) and 30% relative risk reduction in the HF hospitalization (i.e. The HF hospitalization rate per 12 months is 0.6 in the Control group and 0.42 in the Device group).

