#### 5.8.2 Primary Effectiveness Endpoint

That Require Non-elective Cardiovascular Surgery Total

At least ten thousand (10,000) simulations with converged joint frailty model were performed to calculate sample size and power for the primary effectiveness endpoint. With a fixed sample size design, 610 subjects provide approximate 80% power at the one-sided significance level of 5% for the primary effectiveness endpoint.

The following assumptions were made for the calculation of sample size:

- The enrollment rate is based on the actual monthly enrollment numbers from December 2012 to February 2016, then 20 subjects per month, thereafter
- Attrition due to withdrawals at 12 months is 7.5% in both groups
- In the EVEREST High Risk Cohort (N = 211), the lower bound of a 95% confidence interval on the HF hospitalization rate in the period pre-enrollment was ~0.6 per 12 months. The HF hospitalization rate in the Control group is therefore assumed to be 0.6 per 12 months. The HF hospitalization rate in the Device group is assumed to be 0.42 per 12 months (30% Relative Risk Reduction).
- Subjects are followed for a minimum of 12 months. All available follow-up through 24 months at the time of data cut-off will be included in the analysis.
- The mortality rate in the Control group is 27%, and in the Device group is 22%.
- To account for informative censoring of death event, a shared random effect (frailty) model for recurrent events and terminal event is used to simulate recurrent events and

death event data. The correlation between these two processes is introduced by the shared frailty distribution, Gamma distribution with mean of 1 and variance of 1. The frailty is assumed to have the same impact on the hazards for recurrent and terminal event (e.g. frailty exponent is 1). The frailty variance and frailty exponent values are estimated and determined based on the REALISM HR FMR patients data and blinded pooled COAPT roll-in and randomized data as of June, 2016. The key underlying assumptions of the JFM are

- a) The recurrent, terminating, and censoring processes all have continuous distribution so that recurrent events and death cannot happen at the exact same time.
- b) Death event precludes the observation of new recurrent HF hospitalization events, but independent censoring (e.g. withdrawal or lost-to-follow-up) does not interrupt the occurrence of recurrent HF hospitalization events.

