- c) The intensity of the current event process at time *t* is a function of subject's process history, covariates, frailty, and being alive just before time *t*. The intensity of the death process at time *t* is a function of covariates, frailty and being alive just before time *t*. Both recurrent process and death process are correlated through the same frailty distribution.
- d) Censoring (administrative censoring) is noninformative, which does not depend on unobserved frailty.

Detailed information about the joint frailty model assumptions, model specification and analysis method and assumed frailty parameters can be found in a separate appendix to the SAP.

• The Joint Frailty Model method was used to estimate the logarithm of 1-RRR for recurrent HF hospitalization event.

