#### 5.8.4.4 Change in 6MWD at 12 Months

A simulation was performed. Based on the following assumptions, the power is approximate 90% to reject the null hypothesis at the 5% significance level.

- Subjects in the Device group have 30 meters more improvement in the mean change in 6MWD at 12 months from baseline than subjects in the Control group, with standard deviation (SD) of 100 meters for the mean change in 6MWD in each group.
- Assume all-cause mortality rate at 12 months is 27% in the Control group, and 22% in the Device group. Approximate 70% of all-cause deaths in each group are due to cardiovascular reasons. Furthermore, about 70% of cardiovascular deaths are HF related. Thus, it is expected to have approximate 3% difference in HF related cardiovascular deaths at 12 month between two treatment groups (i.e. 10% in the Device group and 13% in the Control group). Subjects who experienced heart failure death prior to 12 months follow-up are assigned with 0 meter of 6MWD at 12 months.
- 10% attrition rate in both groups due to withdrawn or missed visit at 12 months.
- Two-sample *t*-test (it is anticipated that an ANCOVA analysis adjusting for baseline values provides as much as or more power than a two-sample *t*-test).

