#### 5.8.4.6 All-cause Mortality through 24 months (superiority)

A simulation was performed. Assuming the all-cause mortality rate at 12 months is 29% in the Control group, and 19% in the Device group, and 7.5% yearly attrition rate due to withdrawals in both groups, and the constant hazard ratio up to 24 months between two treatment groups, a total of 610 subjects will provide approximate 80% power to detect 10% all-cause mortality difference at 12 months.

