#### **5.8.4.8** All-cause Recurrent Hospitalizations

A simulation was performed. Based on the same assumptions as stated from the primary effectiveness endpoint of recurrent HF hospitalization, a total sample size of 610 subjects provides approximate 80% power to detect 26% relative risk reduction in the HF hospitalization (i.e. the all-cause hospitalization rate per patient per 12 months is 1.9 in the Control group and 1.4 in the Device group). In the simulation, the all-cause mortality rates at 12 months are assumed to be 27% for the Control group and 22% for the Device group.

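### SAP 5.8.4.3 attributes its 84% Finkelstein-Schoenfeld power to the primary endpoint's assumptions (mortality 27%/22%), but the 84% is for 29%/19%; at 27%/22% the same model gives roughly 50-55%

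*SAP*

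**What the plan says.** SAP 5.8.4.3 introduces its simulation with "Based on the same assumptions as stated from the primary effectiveness endpoint" and the Finkelstein-Schoenfeld method. For 610 subjects it reports "approximate 84% power to detect 10% absolute difference in all-cause mortality (i.e. 29% for the Control group and 19% for the Device group"), together with HF hospitalization rates of 0.6 and 0.42 per 12 months.

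The assumptions it points to are in SAP 5.8.2. There, "The mortality rate in the Control group is 27%, and in the Device group is 22" percent. The hospitalization rates are the same 0.6 and 0.42. Death and hospitalization share a frailty with a "Gamma distribution with mean of 1 and variance of 1" and an exponent of 1. SAP 5.8.3.2 shows that 27%/22% are 12-month rates. SAP 5.8.2 adds that model details and "assumed frailty parameters can be found in a separate appendix to the SAP".

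Two other sections help in reading the phrase:
- SAP 5.8.4.8 also invokes the primary endpoint's assumptions, and says "the all-cause mortality rates at 12 months are assumed to be 27% for the Control group and 22% for the Device group".
- SAP 5.8.4.6 (mortality superiority) does not invoke them and lists its own: "Assuming the all-cause mortality rate at 12 months is 29% in the Control group, and 19% in the Device group".

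SAP 5.9 tests the secondary endpoints in a fixed order for labeling claims. The hierarchical endpoint is third of ten and 6MWD is fifth.

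For 6MWD, SAP 5.8.4.4 states that "the power is approximate 90% to reject the null hypothesis at the 5% significance level". SAP 5.6.2.2 and Protocol 7.4.2 also require a point estimate of at least 24 m for the endpoint to be met.

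**The concern.** The stated basis and the mortality rates used do not agree. The absolute mortality difference under the primary assumptions is 27 − 22 = 5 points; the 84% is for 29 − 19 = 10 points. Mortality is the top tier of the hierarchy, so it drives this test strongly. The hospitalization rates do match SAP 5.8.2, so mortality is the printed input that departs.

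A reader who accepts the opening clause will plan on 84% at the third step of the sequence. A failure there stops seven later tests: KCCQ, 6MWD, all-cause hospitalization, NYHA class, LVEDV, mortality superiority and the 30-day composite. The SAP nowhere gives the power of this step under the mortality rates used to size the trial.

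**Working it through.** **Inputs.** 305 per arm; HF hospitalization 0.60 and 0.42 per year; one gamma frailty w (mean 1, variance 1, exponent 1) multiplying both hazards; withdrawal 7.5% per year; follow-up 12 to 24 months (SAP 5.8.2). Pairwise score, tie rule and variance are from SAP 5.6.2.6: T is the sum of Uᵢ over Device subjects, V = n_D(n − n_D)/[n(n − 1)] · ΣUᵢ², and the test rejects for Device if T/√V > 1.96.

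**Not given, so assumed.** Monthly accrual before March 2016, and whether the mortality rates apply before or after averaging over the frailty. Both calibrations were run:
- A (before averaging): λ = −ln(1 − p). This gives 0.342/0.211 at 29%/19% and 0.315/0.248 at 27%/22%. Realized 12-month mortality is λ/(1 + λ): 25.5%/17.4% and 23.9%/19.9%.
- B (after averaging): λ = 1/(1 − p) − 1. Realized mortality equals the printed rates.

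**Results.** 3,000 to 4,000 simulated trials per cell, Monte Carlo SE 0.5 to 0.9 points.

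| Follow-up assumed | Calibration | 29%/19% | 27%/22% |
|---|---|---|---|
| 260 enrolled by February 2016, then 20 a month | A | 84.2% | 50.1% |
| 20 a month throughout | A | 83.8% | 51.0% |
| Last 240 uniform 12-24 months, other 370 at 24 | A | 85.1% | 50.8% |
| All uniform 12-24 months | A | 83.7% | 50.1% |
| All 24 months | A | 86.3% | 50.9% |
| 260 enrolled by February 2016, then 20 a month | B | 90.6% | 55.8% |
| Last 240 uniform 12-24 months, other 370 at 24 | B | 90.6% | 55.0% |
| All uniform 12-24 months | B | 89.2% | 54.8% |

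The plan's figure comes first: calibration A with staggered follow-up reproduces the stated 84%. Changing only mortality then gives 50-51%. The loss is about 35 points under either calibration (85.1 − 50.8 = 34.3; 90.6 − 55.0 = 35.6).

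**Sensitivity.**
- A frailty variance of 0.5, which is not the SAP's value, gives 93.7% and 65.6% under A.
- With no frailty, and accrual as in the first row, the powers are about 99.8% and 83%. That contradicts SAP 5.8.2 and misses the stated 84% at 29%/19%.
- As a weak cross-check, a log-rank test at 29%/19% gives 79.3% under A, 91.1% under B and 95.0% without frailty. SAP 5.8.4.6 states about 80%, but does not mention a frailty.

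**6MWD, supplementary.** Excluding non-HF deaths (22 − 10 = 12% Device, 27 − 13 = 14% Control) and 10% attrition (SAP 5.8.4.4), n = 305 × 0.88 × 0.9 = 242 and 305 × 0.86 × 0.9 = 236.
- *If 30 m and SD 100 describe the whole analysis set:* SE = 100·√(1/242 + 1/236) = 9.15 m. Power to reject is Φ(30/9.15 − 1.96) = 90.6%, matching the stated figure. The significance bound is 1.96 × 9.15 = 17.9 m, so the 24 m rule binds: Φ((30 − 24)/9.15) = 74%, or 77% if ANCOVA reduces the SE by 10%.
- *If they describe survivors only,* with HF deaths then scored 0 m (baseline mean 150-350 m and SD 80-120 assumed, since the SAP gives none): power to reject is 77-88% and both conditions together 77-85%. From a baseline of about 250 m upward the 24 m rule adds almost nothing. These runs leave out subjects unable to exercise for cardiac reasons, whom SAP 5.6.2.2 also scores 0 m.

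**The case against.** The strongest defence is that nothing is concealed. SAP 5.8.4.3 prints 29%/19% in the same sentence as the 84%, and restates hospitalization rates that did not change. It can be read as shared background assumptions followed by a named alternative to detect. SAP 5.8.4.6 uses the same pair for the other mortality-driven test, which suggests a deliberate choice. SAP 5.8.4.8 also states mortality separately after invoking the primary assumptions, which fits a habit of each section naming its own rates.

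Much of this stands. A reader might infer that the 84% is a miscalculation or that the mortality input was hidden. The documents support neither: the figure reproduces at the rates printed beside it. A reader might also infer that the trial is undersized. It was sized on the primary effectiveness endpoint, and SAP 5.10 makes success depend on the two primary endpoints only.

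What does not stand is the opening clause. Where SAP 5.8.4.8 uses it, the mortality that follows is the SAP 5.8.2 pair. In SAP 5.8.4.3 it is not, and no reason is given.

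Precision is also a fair objection. The calibration that reproduces 84% does not realize the printed 29%/19%, and the one that does gives about 90%. The appendix may settle this, so a range is the right headline.

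For 6MWD, it is tempting to call the 90% overstated. It is labelled correctly as power to reject, and SAP 5.6.2.2 discloses the 24 m rule. A joint figure would be additional information, not a correction.

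**Conclusion.** SAP 5.8.4.3 contains an inconsistent power statement. Its 84% holds at 29%/19%. Under the primary assumptions it cites, power is roughly 50-55%, and about 51% under the calibration that returns 84%. The levels rest on the SAP's stated frailty, assumed early accrual and an unseen appendix. The mismatch in the text and a loss of about 35 points under the stated frailty do not depend on the choice between the two calibrations.

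The consequence is for planning labeling claims from the third sequential test onward. Sample size, the primary analysis and type I error are unaffected. On 6MWD, the only point is that the chance of meeting both conditions is not reported; it was below 90% on every reading run.

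**What to change.** In SAP 5.8.4.3:
- Rerun the sponsor's simulation at 27%/22% and report that power beside the 84%. Use one mortality calibration for both and state whether the rates apply before or after averaging over the frailty.
- Reword the basis so that mortality is named as the exception, taken as 29% and 19%, and give the reason. Rewording alone would still leave the power under the trial's own mortality assumption unstated.

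As a supplement in SAP 5.8.4.4, report the probability of meeting both p<0.05 and the 24 m rule beside the 90%. State the baseline 6MWD used, and whether 30 m and SD 100 describe the whole analysis set or survivors only.

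The cost is rerunning two existing simulations and editing two paragraphs. The stated powers will look less favourable. No extra patients are needed, and endpoints, test order and alpha do not change.

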#### 5.8.4.4 Change in 6MWD at 12 Months

A simulation was performed. Based on the following assumptions, the power is approximate 90% to reject the null hypothesis at the 5% significance level.

- Subjects in the Device group have 30 meters more improvement in the mean change in 6MWD at 12 months from baseline than subjects in the Control group, with standard deviation (SD) of 100 meters for the mean change in 6MWD in each group.
- Assume all-cause mortality rate at 12 months is 27% in the Control group, and 22% in the Device group. Approximate 70% of all-cause deaths in each group are due to cardiovascular reasons. Furthermore, about 70% of cardiovascular deaths are HF related. Thus, it is expected to have approximate 3% difference in HF related cardiovascular deaths at 12 month between two treatment groups (i.e. 10% in the Device group and 13% in the Control group). Subjects who experienced heart failure death prior to 12 months follow-up are assigned with 0 meter of 6MWD at 12 months.
- 10% attrition rate in both groups due to withdrawn or missed visit at 12 months.
- Two-sample *t*-test (it is anticipated that an ANCOVA analysis adjusting for baseline values provides as much as or more power than a two-sample *t*-test).

#### 5.8.4.5 NYHA Functional Class of I/II at 12 months

Sample size calculation for the NYHA Functional Class I/II at 12 months was performed using NCSS PASS 11 (Hintze, J., 2011, NCSS, LLC. Kaysville, Utah).

The power calculation for the NYHA Functional Class I/II rate at 12 months is based on the following assumptions:

- Assume 60% of subjects in the Control group had NYHA Functional Class I/II at 12 months, and 75% of subjects in the Device group had NYHA Functional Class I/II at 12 months. Thus, there is 15% more NYHA Functional Class of I/II at 12 months in the Device group than those in the Control group.
- Assume all-cause mortality rate at 12 months is 27% in the Control group, and 22% in the Device group. Approximate 70% of all-cause deaths in each group are due to cardiovascular reasons. Furthermore, about 70% of cardiovascular deaths are HF related. Thus, it is expected to have approximate 3% difference in HF related cardiovascular deaths at 12 month between two treatment groups (i.e. 10% in the Device group and 13% in the Control group). Subjects who experienced heart failure death prior to 12 months follow-up are assigned with NYHA Functional Class IV at 12 months.
- 10% attrition rate in both groups due to withdrawn or missed visit at 12 months.
- Fisher's exact test

With the effective sample size of approximate 220 subjects in each arm at 12 months, there is approximate 90% power to demonstrate that there are more subjects in the Device group who had NYHA Functional Class I/II at 12 months than those in the Control group.

#### 5.8.4.6 All-cause Mortality through 24 months (superiority)

A simulation was performed. Assuming the all-cause mortality rate at 12 months is 29% in the Control group, and 19% in the Device group, and 7.5% yearly attrition rate due to withdrawals in both groups, and the constant hazard ratio up to 24 months between two treatment groups, a total of 610 subjects will provide approximate 80% power to detect 10% all-cause mortality difference at 12 months.

#### 5.8.4.7 Change in Left Ventricular End Diastolic Volume at 12 Months

A simulation was performed. Based on the following assumptions, the power is approximate 80% to reject the null hypothesis at the 5% significance level.

- Assume that subjects in the Device group have 12 mL more reduction in the mean change of LVEDV than subjects in the Control group, with standard deviation (SD) of 45 mL for the change in LVEDV in each group.
- Assume all-cause mortality rate at 12 months is 27% in the Control group, and 22% in the Device group. Approximate 70% of all-cause deaths in each group are due to cardiovascular reasons. Furthermore, about 70% of cardiovascular deaths are HF related. Thus, it is expected to have approximate 3% difference in HF related cardiovascular deaths at 12 month between two treatment groups (i.e. 10% in the Device group and 13% in the Control group). Subjects who experienced heart failure death prior to 12 months follow-up are assigned with the worst observed change in LVEDV at 12 months from baseline
- 20% attrition rate in both groups due to withdrawn, missed visit, or unevaluable echocardiography at 12 months.
- Two-sample *t*-test (it is anticipated that an ANCOVA analysis adjusting for baseline values provides as much as or more power than a two-sample *t*-test).

#### **5.8.4.8** All-cause Recurrent Hospitalizations

A simulation was performed. Based on the same assumptions as stated from the primary effectiveness endpoint of recurrent HF hospitalization, a total sample size of 610 subjects provides approximate 80% power to detect 26% relative risk reduction in the HF hospitalization (i.e. the all-cause hospitalization rate per patient per 12 months is 1.9 in the Control group and 1.4 in the Device group). In the simulation, the all-cause mortality rates at 12 months are assumed to be 27% for the Control group and 22% for the Device group.

#### 5.9 Multiplicity Adjustments

Both the primary safety and primary effectiveness endpoints must be met for trial success.

The secondary endpoints will be evaluated for labeling claims if both primary endpoints are met. The secondary endpoints will be tested sequentially in the following order:

- MR Severity of  $\leq 2+$  at 12 months
- All-Cause Mortality at 12 months (Non-inferiority test)
- Hierarchy of death and recurrent HF hospitalization (analyzed when the last subject completes 12 months of follow-up)
- Change in KCCQ score at 12 months from baseline
- Change in 6MWD at 12 months from baseline
- Recurrent hospitalizations all-cause (analyzed when the last subject completes 12 months of follow-up)
- NYHA Functional Class of I/II at 12 months
- Change in Left Ventricular End Diastolic Volume at 12 months
- All-Cause Mortality (Superiority test, if HR < 1) (analyzed when the last subject completes 12 months of follow-up and use all available data up to 24 months)
- Composite 30-Day Secondary Safety Endpoint

The multiplicity adjustments above are only performed for the primary analyses (ITT) of the primary and secondary endpoints.

